7.2 Lenvatinib

Other names

Lenvima

Classification

LENVIMA, a kinase inhibitor, is the mesylate salt of lenvatinib. Its chemical name is 4-[3-chloro-4-(*N*¹-cyclopropylureido)phenoxy]-7-methoxyquinoline-6-carboxamidemethanesulfonate.

Mode of action

Lenvatinib is a receptor tyrosine kinase (RTK) inhibitor that inhibits the kinase activities of vascular endothelial growth factor (VEGF) receptors VEGFR1 (FLT1), VEGFR2 (KDR), and VEGFR3 (FLT4). Lenvatinib also inhibits other RTKs that have been implicated in pathogenic angiogenesis, tumor growth, and cancer progression in addition to their normal cellular functions, including fibroblast growth factor (FGF) receptors FGFR1, 2, 3, and 4; the platelet derived growth factor receptor alpha (PDGFR α), KIT, and RET.

Storage and Stability

Store at 25°C (77°F); excursions permitted to 15–30°C (59–86°F)

Protocol dose

Lenvatinib is administered at a dose of 20 mg orally.

Preparation

LENVIMA 4 mg capsules are supplied as hard hyperomellose capsules with yellowish-red body and yellowish-red cap, marked in black ink with “€” on the cap and “LENV 4 mg” on the body.

LENVIMA 10 mg capsules are supplied as hard hyperomellose capsules with yellow body and yellowish-red cap, marked in black ink with “€” on the cap and “LENV 10 mg” on the body.

Protocol administration

Lenvatinib is administered orally 20 mg po daily. It will be administered immediately after the Eribulin administration.

Incompatibilities

None

Availability

Lenvima will be supplied by Eisai, Inc in cards containing 10 mg and 4 mg capsules. To order drug, please contact EISAI IIS Department at [contact] or [contact]

Side effects

Detailed information regarding side effects and rates of adverse events of lenvatinib can be found in the package insert. Some of the most common side effects include:

Hypertension

The median time to onset of new or worsening hypertension was 16 days for LENVIMA-treated patients. The incidence of Grade 3 hypertension was 44% as compared to 4% for placebo, and the incidence of Grade 4 hypertension was less than 1% in LENVIMA-treated patients and none in the placebo group.

Cardiac dysfunction

Cardiac dysfunction, defined as decreased left or right ventricular function, cardiac failure, or pulmonary edema, was reported in 7% of LENVIMA-treated patients (2% Grade 3 or greater) and 2% (no Grade 3 or greater) of patients in the placebo group. The majority of these cases in LENVIMA-treated patients were based on findings of decreased ejection fraction as assessed by echocardiography

Hepatic toxicity

4% of LENVIMA-treated patients experienced an increase in alanine aminotransferase (ALT) and 5% experienced an increase in aspartate aminotransferase (AST) that was Grade 3 or greater. No patients in the placebo group experienced Grade 3 or greater increases in ALT or AST. Across clinical studies in which 1108 patients received LENVIMA, hepatic failure (including fatal events) was reported in 3 patients and acute hepatitis was reported in 1 patient.

Other adverse effects include renal failure or improvement, proteinuria, gastro intestinal fistula and perforation, arterial thrombotic events, QT interval prolongation, PRES, hypocalcemia and hemorrhagic events.

Nursing complications

Advise nursing women to discontinue breastfeeding during treatment with LENVIMA

8.0 Statistical Considerations

8.1 Proposed sample size

8.1.1 Safety run in phase

The number of subjects in the safety run-in phase will be 10. In the phase II trial the number of patients will be 30. Three patients will receive lenvatinib at 20 mg qd and Eribulin at 1.4 mg/m² day 1 and day 8 of a 21 day cycle. Eribulin will be given on day 1 and lenvatinib will be started on day 2. If no DLTs are experienced, then the Phase II trial will be initiated at a dose of 24 mg daily of lenvatinib and Eribulin at 1.4 mg/m² day 1 and day 8 of a 21 day cycle. If there is a DLT, then three more patients will be treated at that dose level. If no more DLTs are observed, then the phase II trial can commence at lenvatinib dose of 20 mg qd and Eribulin at 1.4 mg/m² day one and day 8 of a 21 day cycle. If there is another DLT, then there will be a dose reduction of lenvatinib to 14 mg daily.

8.1.2 Phase II

We will use group of n= 30 patients at the MTD. The expected poor response rate is p=0.20 or less, while p>=0.4 or more would be considered successful/good. We intend to proceed by calculating a response rate and providing a 95% confidence interval in the experimental group. This interval will have an approximate half width 2x [0.5/sqrt(30)]= 0.18 or less. We will test the hypothesis that the response rate is larger than 0.2 in the following way: if the lower bound of the one sided 90% exact confidence interval for underlying p is greater than 0.2, we will consider this evidence that p>0.2 i.e. of good response, and worthy of further investigation. Equivalently, using a one sided exact test of H0: p=0.2 versus H1: p>0.2, with power at p=0.4 being over 80%, we have the power analysis below.

Numeric Results for testing H0: P = P0 versus H1: P > P0

Test Statistic: Exact Test

		Given H0	Given H1	Difference	Target	Actual		Reject H0
Power	N	(P0)	(P1)	(P1 - P0)	Alpha	Alpha	Beta	If R>=This
0.8237	30	0.2000	0.4000	0.2000	0.1000	0.0611	0.1763	10

8.2 Data analysis

Data will be analyzed by the PI and [name] using Stata statistical software. We will provide descriptive statistics and confidence intervals for all variables of interest for which data are collected.

8.3 Correlative science

Objective. To quantify serum levels of microRNAs pre- and post-treatment, with the goal of correlating levels with patient response to treatment.

RNA isolation. RNA will be isolated using the mirVanaTM miRNA Isolation Kit (Ambion) and quantified using a Nanodrop spectrophotometer. RNA quality will be determined on an Agilent 2100 Bioanalyzer.

miRNA expression profiling by NGS. We will use the HiSeq 2000 Sequencing System (Illumina) at the GCCRI Genomics Facility to measure miRNA expression profiles. Samples will be barcoded to allow multiplex sequencing and subjected to a second round of Q/C.

Data analysis. Adaptor sequences will be removed and reads of the length ≤ 15 or ≥ 30 are removed as they are not likely to originate from mature miRNAs. Duplicate reads will be removed with the remaining unique reads stored in FASTA format along with the read count. Unique reads will be aligned to the reference human genome (hg19) using the Bowtie short read aligner (0.12.9). Reads mapped to known miRNA loci as defined by miRbase (v21) will be kept for expression profiling. miRNA expression will be derived from counting reads perfectly matching known miRNA loci, normalized to the total number of uniquely mapped reads per sample.

Expected results. Expression profiles of serum miRNAs in 10 responders and 10 non-responders, which can then be compared by t-test to identify differentially expressed miRNAs that correlate with patient response to treatment.

Blood samples for microRNA assay will be collected on Cycle 1, Day 1 of treatment, and at the end of treatment. QIAGEN PAXgene Blood RNA tubes will be used to collect the samples.

Blood samples will be sent to [name] lab:

[name] ([contact])
Greehey Children's Cancer Research Institute
UT Health Science Center at San Antonio
[name]
[name]
T [contact]

Tissue specimens from before and after treatment will be stained for markers of both angiogenesis and of hypoxia, CD-36 and carbonic anhydrase 9 (CA9) respectively, to see if the combination is effective at reducing hypoxia and the effects on angiogenesis. We will also look at the effects on reversal of EMT by performing IHC for E-cadherin, N-cadherin and vimentin to see if there is a reversion with treatment as has been seen in vitro and in animal models.

All IHC will be performed in [name] lab:

UT Health San Antonio
[name]
[name]
[contact]

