2.4.1 Micro RNA assay

Our goal is also to quantify serum levels of microRNAs pre- and post-treatment, with the goal of correlating levels with patient response to treatment.

RNA isolation. RNA will be isolated using the mirVanaTM miRNA Isolation Kit (Ambion) and quantified using a Nanodrop spectrophotometer. RNA quality will be determined on an Agilent 2100 Bioanalyzer. miRNA expression profiling will be determined by NGS. We will use the HiSeq 2000 Sequencing System (Illumina) at the GCCRI Genomics Facility to measure miRNA expression profiles. Samples will be barcoded to allow multiplex sequencing and subjected to a second round of Q/C.

Data analysis. Adaptor sequences will be removed and reads of the length ≤ 15 or ≥ 30 are removed as they are not likely to originate from mature miRNAs. Duplicate reads will be removed with the remaining unique reads stored in FASTA format along with the read count. Unique reads will be aligned to the reference human genome (hg19) using the Bowtie short read aligner (0.12.9). Reads mapped to known miRNA loci as defined by miRbase (v21) will be kept for expression profiling. miRNA expression will be derived from counting reads perfectly matching known miRNA loci, normalized to the total number of uniquely mapped reads per sample.

Expected results. Expression profiles of serum miRNAs in 10 responders and 10 non-responders, which can then be compared by t-test to identify differentially expressed miRNAs that correlate with patient response to treatment.

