3.0 Objective

The overall purpose of this study is to determine the efficacy and safety of the combination of Eribulin, and Lenvatinib in stage 4 breast, NSCLC and sarcoma.

Primary objective

To determine the overall response rate of the combination of lenvatinib and Eribulin

Secondary objectives

- 1) Determine the safety of Eribulin and lenvatinib
- 2) Define the progression free survival
- 3) Expression profile of MicroRNA

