5.3.4 Endpoint Assessment

The overall response rate (ORR) will be defined as response after scans assessed after two cycles of therapy (1 cycle = 3 weeks). Clinical response will be assessed by the treating physician as outlined above. All patients who are on study after 2 cycles will be considered evaluable for the response endpoints.

Progression-free survival (PFS) will be defined as the time from the first study treatment to the first occurrence of progression or death. All patients who receive at least one dose of each drug will be evaluable for this endpoint.

Toxicity will be assessed NCI CTCAE v 4.03. The incidence, nature, and severity of adverse events will be determined. All patients who receive at least one dose of study drug will be considered evaluable for toxicity and safety endpoints.

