16.0 Samples for Correlative Studies

Correlative studies will be conducted as secondary outcome measures to provide information on response prediction. We will perform assays to detect micro RNA and correlate response pre and post treatment.

We will use the HiSeq 2000 Sequencing System (Illumina) at the GCCRI Genomics Facility to measure miRNA expression profiles. Samples will be barcoded to allow multiplex sequencing and subjected to a second round of Q/C.

Blood Sample Collections

1. Red-top vacutainer tubes (not SST), upright at RT for 30 minutes, then centrifuged in a horizontal rotor for 20 min at 1100-1300g. Within 1 hour of centrifugation, pipette aliquots of 150 to 250 ul serum into labeled cryovials. These need to be stored at -80°C and transported on dry ice.
2. Blood samples for microRNA assay will be collected on Cycle 1, Day 1 of treatment, and at the end of treatment. QIAGEN PAXgene Blood RNA tubes will be used to collect the samples and will be stored at -20°C.

Blood samples will be sent to [name] lab:

[name]

Greehey Children's Cancer Research Institute
UT Health San Antonio
[name]
[name]
T: [contact]
Email: [contact]

Tissue specimens from before and after treatment will be stained for markers of both angiogenesis and of hypoxia, CD-36 and carbonic anhydrase 9 (CA9) respectively, to see if the combination is effective at reducing hypoxia and the effects on angiogenesis. We will also look at the effects on reversal of EMT by performing IHC for E-cadherin, N-cadherin and vimentin to see if there is a reversion with treatment as has been seen in vitro and in animal models. Ten unstained slides thickness of 5 micron will be requested from pathology

All IHC will be performed in [name] lab:

UT Health San Antonio
[name]
[name]
[contact]

I Appendix Lenvatinib Package Insert

LENVIMA (lenvatinib) capsules, for oral use

Initial U.S. Approval: 2015

Recommended Dose

The recommended daily dose of LENVIMA is 24 mg (two 10 mg capsules and one 4 mg capsule) orally taken once daily with or without food [see *Clinical Pharmacology* (12.3)].

Continue LENVIMA until disease progression or until unacceptable toxicity occurs.

[figure not shown]
Take LENVIMA at the same time each day. If a dose is missed and cannot be taken within 12 hours, skip that dose and take the next dose at the usual time of administration.

Severe Renal or Hepatic Impairment

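### The microRNA-by-response t-tests have no stated multiplicity rule, and the plan does not say whether baseline level, end-of-treatment level or change is tested

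*Combined protocol and SAP*

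**What the plan says.** Section 3.0 lists "Expression profile of MicroRNA" as the third secondary objective. Section 8.3 gives the aim: "To quantify serum levels of microRNAs pre- and post-treatment, with the goal of correlating levels with patient response to treatment". On what is retained it says "Reads mapped to known miRNA loci as defined by miRbase (v21) will be kept for expression profiling". It names no candidate list and no expression filter. The inferential plan is one sentence, placed under Expected results in the same section: "Expression profiles of serum miRNAs in 10 responders and 10 non-responders, which can then be compared by t-test to identify differentially expressed miRNAs". Its purpose is to find the miRNAs linked to response. Section 2.4.1 repeats it.

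Section 16.0 goes further on purpose: "Correlative studies will be conducted as secondary outcome measures to provide information on response prediction". It adds, as a separate statement: "We will perform assays to detect micro RNA and correlate response pre and post treatment".

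Sections 6.0 (footnote 9), 8.3 and 16.0 fix two blood draws, on Cycle 1 Day 1 and at the end of treatment. Section 8.2, the only general analysis text, promises descriptive statistics and confidence intervals. None of sections 2.4.1, 3.0, 8.2, 8.3 or 16.0 gives an alpha, a multiplicity method, the measurement to be tested, or a statement that the results are exploratory.

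**The concern.** Sequencing keeps every mapped known miRNA, so the t-test is run many times on small groups. If each test is read at a conventional level, about one null miRNA in twenty is flagged. The list of identified miRNAs then mixes true and chance findings in proportions that the plan does nothing to limit.

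The open choice of measurement adds to this. Baseline level, end-of-treatment level and change from one to the other are three different analyses. Running all three triples the expected number of chance hits.

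The choice also matters for the prediction aim in section 16.0. Section 5.3.4 defines the response rate as "response after scans assessed after two cycles of therapy", and section 4.7 lets treatment run to progression or unacceptable toxicity. The end-of-treatment sample therefore normally comes after the response reading, and a later sample cannot predict an earlier result. Only the Cycle 1 Day 1 sample suits that aim. At stake is whether a reader can use the reported miRNA list for a secondary objective.

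**Working it through.** **The plan's own figure.** The documents give no alpha, effect size or power for the miRNA tests. Their only power calculation is the primary one in section 8.1.2: 30 patients, reject at 10 or more responses. The exact binomial gives P(X ≥ 10 | 30, 0.20) = 0.0611 and P(X ≥ 10 | 30, 0.40) = 0.8237, matching the printed table. These are also the chances that 30 patients supply the 10 responders the miRNA comparison expects. At a 30% response rate the chance is 0.41.

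**Inputs.** From section 8.3: 10 against 10, one t-test per miRNA. Assumed, because not stated: two-sided alpha 0.05; 200 to 2,500 tests (m); a true difference (d) of 1 or 2 SD; a share s of 1% to 20% of miRNAs truly associated.

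**Chance hits if nothing is associated.** m × 0.05 gives 200 × 0.05 = 10 up to 2,500 × 0.05 = 125 per analysis.

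**Power per true miRNA, unadjusted.** Noncentral t, 10 + 10 − 2 = 18 degrees of freedom, noncentrality d × √(10 × 10 / 20). At d = 1 SD the power is 0.562; at d = 2 SD it is 0.988.

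**Expected false share of hits.** 0.05(1 − s) / [0.05(1 − s) + power × s]. For s = 0.05 and d = 1: 0.0475 / (0.0475 + 0.0281) = 0.63. The number of tests cancels.

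| Share truly associated | 1 SD | 2 SD |
|---|---|---|
| 1% | 90% | 83% |
| 5% | 63% | 49% |
| 10% | 45% | 31% |
| 20% | 26% | 17% |

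For example, with 200 tests, s = 5% and d = 1, expect 200 × 0.0475 = 9.5 false hits and 200 × 0.05 × 0.562 = 5.6 true ones.

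**With Benjamini-Hochberg at 10%.** Simulation with independent normal data, an equal-variance t-test and 200 or 2,500 tests gives a mean false share of about 8-12%. Power per true miRNA, over s from 1% to 20%:

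| Split | 1 SD | 2 SD |
|---|---|---|
| 10 vs 10 | about 2-21% | not tabulated |
| 10 vs 20 | about 6-44% | about 91% or more |
| 6 vs 24 | about 2-22% | about 71-97% |

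The 6 vs 24 split is what a 20% response rate gives in 30 patients (30 × 0.20 = 6).

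**The case against.** The strongest reply is that this is discovery work and reads that way. Section 8.3 is headed as correlative science, and the t-test appears under Expected results as something that can be done. The Introduction and section 2.3 list the secondary objectives as toxicity, progression-free survival and overall survival, without microRNA. That context is real. It does not outweigh sections 3.0 and 16.0, which make the profile a secondary objective aimed at response prediction, and it does not tell a reader that the hits are unadjusted.

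Three further objections stand and limit the point:

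- A reader might infer that no contrast is specified. Sections 2.4.1 and 8.3 do name it: responders against non-responders. Only the measurement and time point are open.
- A reader might infer that true and chance hits could never be separated. Raw p-values can be adjusted at reporting without new data. What is missing is a rule fixed beforehand.
- A reader might infer that the end-of-treatment sample is of no use. The timing argument applies only to prediction in section 16.0. The aim in sections 2.4.1 and 8.3 is to correlate levels with response before and after treatment, and the later sample can serve that.

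Every size quoted also depends on assumed quantities, and the milder end (17%) belongs in any summary.

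**Conclusion.** The gap is real and minor. The plan tests all mapped miRNAs between responders and non-responders with no multiplicity rule and no stated measurement. If its t-tests are read at an assumed two-sided 0.05 with 10 against 10, the expected false share of hits is 26-90% for a 1-SD difference and 17-83% for a 2-SD difference, as the share truly associated falls from 20% to 1%. A 10% false-discovery rule brings it to about 8-12%. The simulation assumes independent miRNAs, and the documents supply none of alpha, number of tests, effect size or signal share.

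A reader might take these percentages as a threat to the trial's conclusions. The documents do not support that: the primary response-rate test is separate, and no dose, stopping or go/no-go decision uses the miRNA results.

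**What to change.** In sections 2.4.1, 8.3 and 16.0 state that:

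- the prediction analysis compares Cycle 1 Day 1 levels between responders and non-responders, and change to end of treatment is a separate analysis in patients with both samples;
- within each analysis, Benjamini-Hochberg adjusted p-values are reported across all tested miRNAs at a stated false-discovery level (10% is one example; another stated level would serve), and results are hypothesis-generating;
- any expression filter is fixed in advance, applied without response labels, and set no higher than the smaller response group could meet. A filter asking for expression in half of 30 samples (15) would drop a miRNA present in all of 10 responders and in nobody else (10 / 30 = 33%).

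Optionally, use all responders and non-responders with a sample in place of 10 and 10, since 10 or more responders in 30 has probability only 0.06, 0.41 and 0.82 at response rates of 20%, 30% and 40%. If only 20 patients were budgeted, this means sequencing samples already collected from about 10 more patients (30 − 20), or about 20 more if the 10 run-in patients are additional to the 30 (40 − 20), with two samples each.

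The cost is wording, minor analysis work and fewer hits. For a 1-SD difference, power per true miRNA falls from 56% (10 vs 10, unadjusted) to the low figures tabulated above, and an uneven split such as 6 vs 24 does no better than 10 vs 10. Large differences, near 2 SD, remain largely detectable in the two 30-patient splits tabulated.

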3.1 Selection of Patients

The target population for this study is patients with stage IV breast, NSCLC lung cancers and Sarcoma.

This will be a multi-center trial conducted by Mays Cancer Center. At Mays Cancer Center, patients will be recruited by the clinical team in the Breast Center; lung center and sarcoma center. Potential patients may be referred to the Principal Investigator, [name], at [contact].

Eligibility will be evaluated by the study team according to the following criteria. Eligibility waivers are not permitted. Subjects must meet all of the inclusion and none of the exclusion criteria to be registered to the study. Study treatment may not begin until a subject is registered. Please refer to Section 11 for complete instructions regarding registration procedures.

Inclusion Criteria

- Stage IV breast cancer, stage IV NSCLC, stage IV sarcoma
- ECOG PS 0-2
- Measurable disease
- No more than 4 prior chemotherapeutic regimens for metastatic disease
- Patients must be \geq 18 years.
- Patients may not have received Eribulin or lenvatinib previously
- Patients must have a life expectancy of greater than 12 weeks.
- Patients may have had a prior diagnosis of cancer if it has been $>$ 5 years since their last treatment and are considered free of disease.
- Patients must have normal organ and marrow function as defined below:
 - Leukocytes \geq 3,000/ μ L
 - Absolute neutrophil count \geq 1,500/ μ L
 - Platelets \geq 100,000/ μ L
 - Child Pugh score \leq 10
- Patients must be able to swallow and retain oral medication.
- All patients must have given signed, informed consent prior to registration on study.

Exclusion Criteria

- Women who are pregnant or lactating are not eligible for study treatment.
- Patients who are undergoing concomitant radiotherapy are NOT eligible for participation.
- Patients who are receiving any other investigational agents or concurrent anticancer therapy are NOT eligible for participation. Previous systemic treatment and/or radiation therapy is allowed with a 14 day washout period prior to registration.
- Lesions that have been radiated previously cannot be considered target lesions
- Prior treatment related side effects must have resolved to $<$ Grade 2 severity per Common Terminology Criteria for Adverse Events (CTCAE version 4.03), except alopecia and infertility.

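### The planned microRNA t-test pools three tumour types without adjustment and leaves the count scale unstated, so tumour-type differences can produce false response markers or hide real ones.

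*Combined protocol and SAP*

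**What the plan says.** Section 8.3 sets out the microRNA analysis in three steps.

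- **Measure:** "miRNA expression will be derived from counting reads perfectly matching known miRNA loci", then "normalized to the total number of uniquely mapped reads per sample".
- **Expected groups:** "Expression profiles of serum miRNAs in 10 responders and 10 non-responders".
- **Test:** the groups are "compared by t-test to identify differentially expressed miRNAs that correlate with patient response to treatment".

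Section 2.4.1 repeats the pipeline and the test ("which can then be compared by t-test to identify differentially expressed miRNAs"). The patients come from three populations (Section 3.1: "Stage IV breast cancer, stage IV NSCLC, stage IV sarcoma"), with no quota by type. Section 8.2 adds only a general statement: "We will provide descriptive statistics and confidence intervals for all variables of interest for which data are collected".

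No section mentions tumour type as a covariate, stratum or subset for this analysis. None says whether the normalised counts are logged or fitted with a count model. No significance level is given for the screen. Samples are taken on Cycle 1 Day 1 and at the end of treatment, and the plan does not say which time point, or what change between them, enters the t-test.

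MicroRNA expression is a listed secondary objective (Section 3.0), and Section 16.0 gives its purpose: "Correlative studies will be conducted as secondary outcome measures to provide information on response prediction".

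**The concern.** Tumour type may be related both to the level of a serum microRNA and to the chance of response. If it is related to both, a pooled two-group comparison attributes the type difference to response. If it is related only to the microRNA, the spread between types stays in the error term and the test loses power. Either way the plan contains no step that separates the two.

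The protocol's own background shows that response to lenvatinib varies widely by tumour. Section 2.2 reports 64.8% in differentiated thyroid cancer, 36% in medullary thyroid cancer, 14.3% in endometrial cancer and 9% in melanoma (the last three by independent review). These are not the three enrolled types and not the combination, so they make a difference by type plausible without giving its size.

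Scale is a second, smaller issue. Read counts divided by library size tend to be right-skewed, and a t-test on that scale with about 10 per group is inefficient at the small p-values that a screen of many microRNAs calls for.

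At stake is whether a reported response marker can be read as one, and whether the available samples are used well.

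**Working it through.** **The plan's own figure.** The plan states no power, alpha, effect size or SD for the t-test. The nearest stated figure is the phase II rule in Section 8.1.2 (N = 30, reject at 10 or more responses). Exact binomial tails give alpha 0.0611 at p = 0.2 and power 0.8237 at p = 0.4, as stated. The same tails give the chance of having the 10 expected responders among 30 patients: 0.061 at p = 0.2, 0.411 at p = 0.3 and 0.824 at p = 0.4.

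**Hand check, 10 v 10.** Let log expression have SD 1 within type, with a shift of D in breast only (assumed). The counts below are breast/NSCLC/sarcoma. The t-test uses 18 df, with critical value 2.101. With the mix fixed, the true standard error of the mean difference is sqrt(2/10) = 0.447.

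*Unequal mix, 6/2/2 responders v 2/4/4 non-responders, no response effect, D = 2.*
- Expected difference: 2 × (0.6 − 0.2) = 0.8.
- Pooled variance seen by the t-test: 1 + 4 × (2.4 + 1.6)/18 = 1.889, so its standard error is 1.374 × 0.447 = 0.615.
- Rejection needs a difference above 2.101 × 0.615 = 1.292. P(Z > (1.292 − 0.8)/0.447) = P(Z > 1.10) ≈ 0.14. Simulation gives 0.16.

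*Equal mix, 4/3/3 in both groups, true response effect 1.32, D = 2.*
- Pooled variance: 1 + 4 × (2.4 + 2.4)/18 = 2.067, so the standard error is 1.438 × 0.447 = 0.643.
- Rejection needs a difference above 1.351. P(Z > (1.351 − 1.32)/0.447) ≈ 0.47. Simulation gives 0.49, against 0.79 with type in the model.

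**Simulation, fixed mixes, 10 v 10, two-sided 0.05, no response effect.**

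| Responders v non-responders | D = 1 | D = 2 | D = 3 | Adjusted for type |
|---|---|---|---|---|
| 4/3/3 v 4/3/3 | 0.029 | 0.006 | 0.000 | about 0.05 |
| 5/3/2 v 3/3/4 | 0.047 | 0.029 | 0.012 | about 0.05 |
| 6/2/2 v 2/4/4 | 0.10 | 0.16 | 0.20 | about 0.05 |
| 7/2/1 v 2/4/4 | 0.14 | 0.30 | 0.44 | about 0.05 |

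**Simulation, random response, 30 patients, 10 per type (assumed).**

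| Assumed response by type | Quantity | D = 1 | D = 2 | D = 3 | Adjusted |
|---|---|---|---|---|---|
| 50/20/20% | false positives | 0.11 | 0.23 | 0.30 | about 0.05 |
| 40/30/20% | false positives | 0.07 | 0.10 | 0.11 | about 0.05 |
| 30/30/30% | false positives | about 0.05 | about 0.05 | about 0.05 | about 0.05 |
| 30/30/30% | power, 1.32 SD effect | 0.79 | 0.64 | 0.42 | 0.83–0.86 |

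A repeat of the last row with 8,000 runs gave 0.80, 0.61 and 0.42 unadjusted and 0.84 to 0.85 adjusted, so the unadjusted values are best read as roughly 0.8, 0.6 and 0.4.

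**Scale, 10 v 10, power of the t-test on raw v logged counts (spread and fold change assumed).**

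| Threshold | Setting | Raw | Logged |
|---|---|---|---|
| p < 0.001 | log-normal, SD of ln 0.7, 4-fold | 0.28 | 0.67 |
| p < 0.001 | log-normal, SD 1.0, 4-fold | 0.04 | 0.26 |
| p < 0.001 | negative binomial, dispersion 0.5, 4-fold | 0.30 | 0.52 |
| p < 0.05 | log-normal, SD 0.5, 2-fold | 0.78 | 0.83 |
| p < 0.05 | log-normal, SD 1.0, 3-fold | 0.43 | 0.64 |
| p < 0.05 | log-normal, SD 1.5, 4-fold | 0.20 | 0.50 |
| p < 0.05 | negative binomial, dispersion 0.5, 4-fold | 0.96 | 0.95 |

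With no true difference, the raw-scale t-test at 0.05 rejects at 0.024 to 0.046, so skewness alone makes it conservative.

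**The case against.** Four points can fairly be made for the plan.

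1. *The text does not say that the counts are unlogged.* This stands. Normalised counts are the literal reading, but nothing rules out logging first. A reader might infer that the plan prescribes an unlogged t-test; the documents support only that no scale is specified.
2. *The false positives depend on chosen settings.* This stands. They need a type-dependent microRNA and a clear difference in type mix between responders and non-responders. With equal response rates there is no excess, and with the mild fixed imbalance of 5/3/2 v 3/3/4 the unadjusted test is at or below 5%. The documents give no response rates for the combination by type and no microRNA data by type. A reader might infer that any hits will be tumour-type markers, or could never be told apart from them. Neither follows: the excess is conditional, and because tumour type is known, hits can be tabulated by type afterwards. That would still be an unplanned check at the analyst's discretion.
3. *The contrast may be within-patient change.* Section 8.3 aims at pre- and post-treatment levels. If the analysed quantity is change on the log scale, a constant type shift cancels, and the confounding shown above goes with it. This stands as a limit, and it is also a reason to state the contrast.
4. *The analysis is exploratory and correlative, and the t-test is described under expected results.* This lowers the priority. It does not remove the point, because the t-test is the only comparison the plan names for a listed secondary objective.

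**Conclusion.** The concern holds in a conditional form. The named test ignores tumour type. If microRNA level at the compared time point varies by type, the unadjusted t-test either over-rejects (about 11% to 30% at 50/20/20% assumed response and 1 to 3 SD shifts, about 7% to 11% at 40/30/20%) or loses power (to roughly 0.8, 0.6 and 0.4, against 0.83 to 0.86, at equal 30% response). If level does not vary by type, neither problem arises.

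The unstated scale is an omission. Its cost, should the test be run unlogged, is a loss of power that is clear at p < 0.001 and ranges from none to about 30 points at p < 0.05. It is not a source of false positives.

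The sizes rest on assumed response splits, type shifts, spreads and fold changes, and on 10 patients per type in the random-response runs. The primary response-rate test is unaffected. This is a worthwhile, inexpensive improvement to a secondary, exploratory analysis.

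**What to change.** In Sections 2.4.1 and 8.3, replace the t-test with one of these, fitted per microRNA with response and tumour type as factors, and report the response coefficient:

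- a linear model on log2(counts per million + a small offset); or
- a negative-binomial count model.

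Rescaling to counts per million must come before the log. On the plan's literal fraction of total reads, adding 1 and logging changes nothing: with an assumed 100 reads in 1 million, x = 0.0001 and log2(1 + x) ≈ x/ln 2, which is linear in x. In simulation, power at p < 0.001 (SD 0.7, 4-fold) is then the same as on the raw scale, 0.28 in both.

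Also state what is compared: the Cycle 1 Day 1 level, which suits response prediction, or within-patient log change.

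Cost: wording only, since tumour type is known from eligibility. The model spends 2 degrees of freedom (18 to 16 in a 10 v 10 comparison). If there is in fact no type effect and types are imbalanced between the groups, power for a 1.32 SD effect falls from about 0.80 to 0.72 (6/2/2 v 2/4/4) or 0.66 (7/2/1 v 2/4/4).
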